5.2 AEs coding/grading

Adverse events are coded using the Medical dictionary for regulatory activities (MedDRA) terminology. AEs will be categorized as mild, moderate, or severe.

5.3 Laboratory parameters derivations

Central laboratory assessments:

The central laboratory will flag on the central laboratory report all values falling outside of the central laboratory normal ranges

Vital and ECG signs:

Clinically notable values for vital signs are defined as:

- heart rate of < 50 and > 100 bpm
- systolic blood pressure of < 90 and ≥ 140 mmHg
- diastolic blood pressure of < 60 and ≥ 90 mmHg
- history of long QT syndrome or resting QTcF (Fridericia) prolonged (>450 ms for males or >460 ms for females)
- QT increase from baseline \geq 60msec

5.4 Statistical models

The mean responses at treatment group will be obtained through covariate-adjusted treatment effects by using a MMRM as specified in Section 2.5.2 and Section 2.6.2. The model will be fitted using the SAS procedure "PROC MIXED". For SjS MMRM related model, the unstructured covariance matrix will be used (TYPE = UN), thus allowing adjustment for correlations between time points within participants. In order to get the variance covariance matrix of treatment effects to be full rank matrix, no intercept option will be used (NOINT option in MODEL statement).

Adjusted means and the corresponding variance covariance matrix will be estimated. The estimated treatment differences for treatment comparisons will be tabulated along with the associated 95% confidence intervals (two-sided ALPHA = 0.05) and one-sided p-value. No adjustment for multiplicity will be made. For calculation of denominator degrees of freedom Kenwood-Rogers method would be used (DDFM=KR).

In case the MMRM model does not converge the following sequential steps will be used:

- 1. change ddfm=kr to ddfm=bw. If still no convergence, perform step 2.
- 2. change type=un to type=cs. If still no convergence, perform step 3. This is for SjS analysis
- 3. remove covariates in the following order until convergence: stratification factor, treatment group by visit interaction.

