2.5.2 Statistical hypothesis, model, and method of analysis

SjS

The change from baseline in ESSDAI is assumed to be normally distributed. A mixed effect model for repeated measurements (MMRM) will be fitted to the changes from baseline in ESSDAI for all time points until Week 24, with the following fixed effects:

- treatment group
- visit as categorical variable
- treatment group by visit interaction

and baseline ESSDAI as continuous covariate. An unstructured variance-covariance matrix will be fitted to model the dependency between repeated observations. If not possible, other appropriate covariance structures will be explored.

The difference between MHV370 and placebo in change from baseline at each visit will be estimated from the model and presented with 95% confidence intervals and one-sided p-value.

The following two criteria will be used to assess treatment efficacy:

- a statistically significant reduction in ESSDAI at Week 24 in the MHV370 group compared to placebo, at the one-sided 10% significance level, and
- an estimated mean reduction in ESSDAI at Week 24 in the MHV370 group to be at least 2 points greater than in placebo.

A positive sign of efficacy will be considered if both criteria are met.

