3.1 Primary endpoint(s)

SjS

A total of approximately 48 participants with SjS will be randomized in a 1:1 ratio to MHV370 or placebo, with the aim to have at least 40 participants completing Week 24 assessment.

With 40 participants in the analysis of the primary efficacy variable (20 in MHV370 and 20 in placebo), the study would have approximately 80% chance of meeting both efficacy criteria, when the true difference between MHV370 and placebo is 3.5 points. In case the difference between MHV370 and placebo is zero points, the study would have approximately 10 % chance of meeting both efficacy criteria.

These calculations are based on assumed standard deviation of 5.1 in change from baseline in ESSDAI, based on data from TEARS study with rituximab (Devauchelle-Pensec et al 2014).

MCTD

A total of approximately 12 participants with MCTD will be randomized in a 1:1 ratio to MHV370 or placebo. The sample size was chosen for logistical reasons and no sample size calculations were made.

4 Change to protocol specified analyses

No change from protocol specified analysis was made.

5 Appendix

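### SAP 5.4 fallback: step 1 (KR to BW) cannot affect convergence, and step 2 (UN straight to CS) can misstate the Week 24 standard error in either direction

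*SAP*

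**What the plan says.** SAP 2.5.2 specifies an MMRM for change in ESSDAI with treatment, visit, their interaction and baseline ESSDAI, and an unstructured covariance matrix. If that cannot be fitted, it says "If not possible, other appropriate covariance structures will be explored". Success at Week 24 has two criteria. One is significance against placebo on a one-sided 10% test. The other is a threshold for the point estimate: "an estimated mean reduction in ESSDAI at Week 24 in the MHV370 group to be at least 2 points greater than in placebo".

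SAP 5.4 gives the implementation: PROC MIXED, TYPE=UN and DDFM=KR. For non-convergence it lists sequential steps. Step 1 is "change ddfm=kr to ddfm=bw. If still no convergence, perform step 2". Step 2, for SjS, is "change type=un to type=cs. If still no convergence, perform step 3". Step 3 removes model terms and is not at issue here.

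No structure between UN and CS is named, and no robust standard error. SAP 2.6.2 uses the same kind of model for ESSPRI, FACIT-F, PhGA, Schirmer's test and salivary flow. Protocol 12.4.5 mentions simpler structures for SjS, but under sensitivity analyses.

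**The concern.** **Step 1.** Non-convergence is a failure to maximise the REML likelihood over the covariance parameters. DDFM is not part of that likelihood. It sets the degrees of freedom, and for KR the standard-error adjustment, once the covariance parameters have been estimated. Changing it leaves the failed optimisation as it was. As the steps are sequential and KR is never restored, BW also stays in force at step 2.

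**Step 2.** CS has a single variance for Weeks 4, 8, 12, 20 and 24. The Week 24 standard error then rests on an average over visits. If the Week 24 residual variance differs from that average, the p-value and interval for the one visit that matters are wrong.

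At stake, if the fallback is reached, are the Week 24 p-value and 95% CI for the primary endpoint, and the same outputs for the SjS secondary endpoints.

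**Working it through.** **Inputs from the documents.** One-sided alpha 0.10 and the 2-point criterion (SAP 2.5.2); 20 analysed per arm, SD of change 5.1, true difference 3.5 (SAP 3.1); post-baseline visits at Weeks 4, 8, 12, 20 and 24 (Protocol 12.4). Only one SD is given, so the visit-specific SDs and correlations below are assumptions.

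**Reproducing the plan's figures.** SE = 5.1 × √(2/20) = 1.613. Criterion 1 needs an observed difference of 1.2816 × 1.613 = 2.07, just above the 2-point criterion.
- At a true difference of 3.5, the chance of meeting both criteria is 81.3% (normal) or 79.8% (t, 38 df). The SAP says "approximately 80% chance of meeting both efficacy criteria".
- At zero difference it is 10.0% (normal) or 9.3% (t). The SAP says "approximately 10 % chance of meeting both efficacy criteria".

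Both figures reproduce.

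**CS by hand.** With complete data, CS replaces the Week 24 variance by roughly the mean of the five visit variances. Let r = √(mean variance)/5.1. The nominal 10% test then has a level of about P(Z > 1.2816 r), and the 95% CI covers with probability about P(|Z| < 1.96 r). SDs are taken as linear across the five visits.

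| SD, Week 4 to Week 24 | Mean variance | r | One-sided level | 95% CI coverage |
|---|---|---|---|---|
| 5.1 flat | 26.01 | 1.000 | 10.0% | 95.0% |
| 4.1 to 5.1 | 106.425/5 = 21.285 | 0.905 | 12.3% | 92.4% |
| 3.1 to 5.1 | 86.55/5 = 17.31 | 0.816 | 14.8% | 89.0% |
| 6.1 to 5.1 | 157.425/5 = 31.485 | 1.100 | 7.9% | 96.9% |

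**Simulation with dropout.** REML fits of the full model, 24 per arm falling to 20 at Week 24, 1,500 null trials per row. Monte Carlo error on each rate is √(0.1 × 0.9/1500) = 0.8 points. BW-type tests use between-subject df.

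| SD pattern, correlation | UN+KR: SE, level | UN+BW: level | CS: SE, level | CS: both criteria |
|---|---|---|---|---|
| flat, CS 0.6 | 1.567, 10.9% | 11.0% | 1.567, 10.5% | 9.8% |
| flat, AR 0.8 | 1.574, 10.5% | 10.6% | 1.559, 10.5% | 9.8% |
| 4.1 to 5.1, AR 0.8 | 1.571, 10.3% | 10.4% | 1.401, 12.9% | 10.3% |
| 3.1 to 5.1, AR 0.8 | 1.571, 10.2% | 10.5% | 1.257, 15.5% | 11.1% |
| 3.1 to 5.1, CS 0.6 | 1.560, 9.7% | 9.9% | 1.263, 15.0% | 10.3% |
| 6.1 to 5.1, AR 0.8 | 1.577, 10.4% | 10.7% | 1.726, 8.6% | 8.5% |

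- *Step 1 alone:* KR and BW share the same fit and estimate, and the levels differ by 0.3 points or less.
- *Step 2:* the SE is 11% too small for 4.1 to 5.1 (1.401/1.571 = 0.89), 20% too small for 3.1 to 5.1 (1.257/1.571 = 0.80), and 9% too large when the SD falls (1.726/1.577 = 1.09). Within-subject df under CS adds 0.3 to 0.7 points.

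**Why the 2-point criterion helps.** Whatever SE is reported, both criteria cannot be met unless the observed difference reaches 2. With a true SE of 1.613 and no effect, that has probability P(Z > 2/1.613) = 10.7%. The cap loosens as the true SE grows: at residual SD 7.0, SE = 7 × √(2/20) = 2.21 and the bound is 18.3%. In a simulation at that SD with rising variance, the both-criteria rate went from 9.9% to 12.8%. SD 7.0 is above the SAP's planning value and is shown only to mark the limit of the protection.

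**The case against.** **A reader might infer that CS always understates the Week 24 standard error.** The documents do not support that. It holds only if residual variance rises to Week 24. Growth in the variance of a change score over time is plausible, but the SAP gives one SD and none by visit. With a flat SD there is no understatement, and with a falling SD the test is conservative.

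**A reader might also infer that the SjS efficacy decision is materially inflated.** At the planning SD it is not: both criteria are met in about 11% of null trials or fewer. If 5.1 is the SD of change and the baseline-to-Week 24 correlation is 0.50 with equal SDs, the baseline-adjusted residual SD is 5.1 × √0.75 = 4.42. Under rising variance the both-criteria rate was then 8.1% for a Week 24 ANCOVA and 8.3% for CS, which is practically no change.

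**The fallback may never be used.** UN converged in every simulated trial above. Those trials used normal data and at least 20 per arm at Week 24. The planned interim, at about 50% of SjS completers, would estimate 15 covariance parameters (5 × 6/2) from about 24 completers plus partial data. Values after intercurrent events, and ESSDAI totals with a missing domain, are also set to missing. The need is uncertain, not excluded.

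**SAP 2.5.2 and 5.4 can be read as general text and detail.** That is fair, and they need not be called contradictory. But one leaves the structure open and the other fixes it, with no cross-reference. The SAP's sensitivity section is redacted, so further provision there cannot be ruled out.

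**The sizes do not carry over to every secondary endpoint.** Schirmer's test and salivary flow are measured at only three post-baseline visits (Weeks 4, 12 and 24), and no secondary success threshold is visible.

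**Conclusion.** The point stands in limited form.

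- **Step 1** is a pre-specified remedy that cannot do what it is listed to do. Its numerical cost is small: about 0.3 points of type I error or less.
- **Step 2** can give a wrong Week 24 standard error in either direction. With a Week 24 SD of 5.1 and about 20 per arm, the one-sided 10% test runs at about 10% (flat SD), 12-15% (rising from 4.1 or 3.1) or 8-9% (falling from 6.1). These ranges rest on assumed visit SDs, normal data and the fallback being reached.
- **The two-criterion decision** stays at about 11% or less at SD 5.1. The reported p-value and 95% CI, and the SjS secondary models, have no second criterion to limit the error.

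The case for changing the text is that equal variance is an untested assumption at the only visit that decides success, and it is cheap to avoid.

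**What to change.** 1. Delete step 1 and keep DDFM=KR for all model-based fits. If a failure of the KR computation after a converged fit was meant, say so; that is a different event.
2. Replace step 2 with a fixed order of heterogeneous-variance structures, for example TOEPH, then ARH(1), then CSH, stopping at the first that converges. TOEPH and ARH(1) treat visits as equally spaced, which Weeks 4, 8, 12, 20 and 24 are not; CSH does not depend on spacing. The SAP should acknowledge this when it fixes the order.
3. If CS is kept as a last resort, label it as assuming equal variances. If a sandwich standard error is used with it, pair it with a compatible DDFM and a small-sample correction. KR adjusts the model-based covariance and does not combine with a sandwich estimator. The correction matters: an uncorrected sandwich gave 10.7-11.3% in simulation at 20 per arm, and with flat variance it did worse than plain CS (about 11.1% against 10.0-10.3%).
4. Make SAP 2.5.2, and the matching sentence in 2.6.2, refer to this list.

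Cost: a few lines of SAP text and code. If UN converges, no result changes.

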1.2.1 Primary estimands

The estimand is the precise description of the treatment effect and reflects strategies to address events occurring during trial conduct which could impact the interpretation of the trial results (e.g. premature discontinuation of treatment).

SjS

The primary clinical question of interest is: What is the effect of MHV370 on change in ESSDAI total score after 24 weeks of treatment in participants with moderate to severe Sjögren's Syndrome who are receiving a stable dose of a certain concomitant medication (systemic corticosteroid treatment, azathioprine, methotrexate, leflunomide,

Novartis	Confidential	Page 9 of 34
SAP		Study No. CMHV370A12201

hydroxychloroquine (HCQ) and chloroquine (CQ)), had treatment continued for the entire 24 week duration, had no dose change in certain allowed concomitant medication occurred and had no prohibited medication been taken?

The justification for the primary estimand is that wish to estimate the effect of the study drug for the full treatment duration when administered without dose changes in certain allowed concomitant medication (systemic corticosteroid treatment, azathioprine, methotrexate, leflunomide, HCQ and CQ) and without intake of prohibited medication.

The primary estimand is described by the following attributes:

- 1. Population: Participants with moderate to severe Sjögren's Syndrome receiving a stable dose of a certain concomitant medication (systemic corticosteroid treatment, azathioprine, methotrexate, leflunomide, HCQ and CQ).
- 2. Endpoint: Change from baseline in ESSDAI total score at Week 24.
- 3. Treatment of interest: the randomized treatment (investigational treatment MHV370 or placebo) with or without the allowed concomitant medication.
- 4. Handling of remaining intercurrent events:
 - Treatment discontinuations for any reason: had participants taken the assigned treatment for the entire study duration (hypothetical strategy).
 - Unforeseen change in the dose of certain allowed concomitant medication: had no change in the dose of systemic corticosteroid treatment, azathioprine, methotrexate, leflunomide, HCQ and CQ occurred (hypothetical strategy).
 - Intake of prohibited medication: had no prohibited medication been taken (hypothetical strategy).
- 5. The summary measure: Difference in mean change from baseline in ESSDAI total score at Week 24 between treatments.

MCTD

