The primary clinical question of interest is: What is the effect of MHV370 on change in PhGA after 24 weeks of treatment in participants with MCTD who are receiving a stable dose of a certain concomitant medication (systemic corticosteroid treatment, azathioprine, methotrexate, leflunomide, HCQ and CQ), had treatment continued for the entire 24 week duration, had no dose change in certain allowed concomitant medication occurred and had no prohibited medication been taken?

The justification for the primary estimand is that wish to estimate the effect of the study drug for the full treatment duration when administered without dose changes in certain allowed concomitant medication (systemic corticosteroid treatment, azathioprine, methotrexate, leflunomide, HCQ and CQ) and without intake of prohibited medication.

The primary estimand is described by the following attributes:

- 1. Population: Participants with MCTD receiving a stable dose of certain concomitant medication (systemic corticosteroid treatment, azathioprine, methotrexate, leflunomide, HCQ and CQ).
- 2. Endpoint: Change from baseline in PhGA at Week 24.

Novartis	Confidential	Page 10 of 34
SAP		Study No. CMHV370A12201

- 3. Treatment of interest: the randomized treatment (investigational treatment MHV370 or placebo) with or without the allowed concomitant medication.
- 4. Handling of remaining intercurrent events:
 - Treatment discontinuations for any reason: had participants taken the assigned treatment for the entire study duration (hypothetical strategy).
 - Unforeseen change in the dose of certain allowed concomitant medication: had no change in the dose of systemic corticosteroid treatment, azathioprine, methotrexate, leflunomide, HCQ and CQ occurred (hypothetical strategy).
 - Intake of prohibited medication: had no prohibited medication been taken (hypothetical strategy).
- 5. The summary measure: Difference in mean change from baseline in PhGA at Week 24 between treatments.

2 Statistical methods

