2.5 Analysis supporting primary objective(s)

All participants within the PD analysis set will be included for the primary analyses.

2.5.1 **Primary endpoint(s)**

SjS

The primary endpoint is the change from baseline in ESSDAI total score at Week 24, defined as the Week 24 visit ESSDAI total score minus the baseline ESSDAI total score. A negative change indicates an improvement of disease activity. Details for the derivation of ESSDAI total score can be found in Appendix 5.4.1.1.

The ESSDAI score for SjS participants will be listed by treatment group, participant and visit/time. Descriptive statistics (raw and change from baseline) will be provided by treatment group and visit/time. Graphical methods, such as spaghetti plots up to Week 24, may be employed by treatment and visit/time. In addition, bar plots will be used to visualize (1) the contribution of the individual ESSDAI domains to the estimated change from baseline in the total ESSDAI score by treatment group and visit/time and (2) the difference in the contribution of the individual ESSDAI domains to the estimated change from baseline in the total ESSDAI score by treatment groups by visit/time.

MCTD

The primary endpoint is the change from baseline in PhGA (ranging from "no disease activity" (0) to "maximal disease activity" (100)) after 24 weeks of treatment. It is defined as the Week 24 visit PhGA value minus the baseline PhGA value. A negative change indicates an improvement in disease activity. The PhGA score for MCTD participants, will be listed by treatment group, participant and visit/time. Descriptive statistics (raw and change from baseline) will be provided by treatment group and visit/time. Graphical methods, such as spaghetti plots up to Week 24, may be employed by treatment and visit/time.

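### The last step of the SAP's non-convergence rule drops treatment-by-visit, so in SjS the model could no longer estimate the Week 24 difference; the step is very unlikely to be reached (minor)

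*SAP*

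**What the plan says.** SAP 1.2.1 defines the SjS summary measure as "Difference in mean change from baseline in ESSDAI total score at Week 24 between treatments". SAP 2.5.2 fits treatment, visit, treatment-by-visit and baseline ESSDAI with an unstructured covariance matrix, and adds: "If not possible, other appropriate covariance structures will be explored". On output it says: "The difference between MHV370 and placebo in change from baseline at each visit will be estimated from the model". There are two efficacy criteria, both at Week 24: significance at the one-sided 10% level, and "an estimated mean reduction in ESSDAI at Week 24 in the MHV370 group to be at least 2 points greater than in placebo".

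SAP 5.4 covers the models of sections 2.5.2 and 2.6.2 and states: "In case the MMRM model does not converge the following sequential steps will be used". Step 1 changes the degrees-of-freedom method. Step 2, marked as applying to SjS, replaces the unstructured matrix by compound symmetry. Step 3 is to "remove covariates in the following order until convergence: stratification factor, treatment group by visit interaction".

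Neither Protocol 12.4.2 nor SAP 2.5.2 lists a stratification factor in the SjS primary model. Protocol 12.4.2 lists one, pulmonary involvement, for MCTD.

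**The concern.** Step 3 calls the interaction a covariate, but it is the term that lets the treatment difference vary by visit. Without it, software can still print a Week 24 difference, but that number is forced to equal the one at every other visit.

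In the SjS primary analysis there is no stratification factor to remove first, so step 3 goes straight to the interaction. The Week 24 criteria would then be applied to a visit-averaged quantity, and nothing in the visible text says that the target has changed. The result can mislead in either direction: an effect that builds up late is understated, and one that has faded by Week 24 is overstated.

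**Working it through.** **Inputs from the documents.** SAP 3.1: 20 analysed per arm, SD 5.1, true difference 3.5, about 80% chance of meeting both criteria, and about 10% if the true difference is zero. SAP 2.5.2: one-sided 10% level and a 2-point minimum estimate. Protocol 12.4: post-baseline visits at Weeks 4, 8, 12, 20 and 24.

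**Inputs assumed.** The time course of the effect; a common within-participant correlation ρ of 0.4, 0.6 or 0.8; SD 5.1 at every visit.

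**Step 1: the plan's own figure** (normal approximation).
- SE at Week 24 = 5.1 × √(2/20) = 1.613.
- Smallest significant difference = 1.2816 × 1.613 = 2.07, slightly above 2, so significance is the binding criterion.
- Chance of meeting both criteria at 3.5 points: Φ((3.5 − 2.07)/1.613) = 81%. At zero: 10%. The stated figures reproduce.

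**Step 2: what the reduced model estimates.** In SjS, step 3 follows compound symmetry. With complete data the single treatment coefficient is then the plain mean of the five visit differences, with SE = 1.613 × √((1 + 4ρ)/5).
- ρ = 0.4, 0.6, 0.8 gives SE = 1.16, 1.33, 1.48.
- Smallest significant difference = 1.2816 × SE = 1.49, 1.70, 1.89. All are below 2, so the 2-point criterion now binds, and the chance of meeting both is Φ((mean − 2)/SE).

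A fitted example (20 per arm, five visits, random intercept) confirms the averaging. With the interaction the differences were −2.49, −2.36, −3.17, −2.10 and −5.10. Without it, −3.044 at every visit, which is their mean.

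**Step 3: size under assumed time courses, complete data.**

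| True effect | Visit mean | Both criteria, reduced model | Both criteria, Week 24 contrast |
|---|---|---|---|
| Linear rise to 3.5 at Week 24 | 3.5 × 68/(5 × 24) = 1.98 | 49–50% | 81% |
| 3.5 at Weeks 4–12, zero at Weeks 20–24 | 3 × 3.5/5 = 2.10 | 53% | 10% |
| Constant 3.5 | 3.50 | 85–90% | 81% |
| Zero at all visits | 0 | 4–9% | 10% |

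**Step 4: with dropout.** Assume 24 per arm with one participant lost after each of Weeks 4, 8, 12 and 20, leaving the planned 20. Early visits then gain weight: Week 4 has 24–25% and Week 24 has 17%. The linear rise gives 1.84–1.87 and about 45% success. The early effect gives 2.25–2.28 and 58–59%.

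**Step 5: how likely the branch is.** In 120 simulated SjS trials (48 participants, 25% monotone missingness, a purpose-written REML optimiser, not PROC MIXED), neither the unstructured nor the compound-symmetry fit failed. Zero failures in 120 puts the failure rate of each below about 3/120 = 2.5%.

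**The case against.** The strongest objection is weight. Both the unstructured and the compound-symmetry fits must fail, neither did so in simulation, and removing a fixed effect rarely cures a covariance problem. The percentages also depend on assumed time courses, one of which is deliberately unfavourable. All of this stands and fixes the severity as minor. It does not make the rule correct: a prespecified last step should still answer the stated question.

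Four stronger readings are tempting, and the documents do not support them.

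- *Both estimands are lost.* The MCTD estimand is also a Week 24 quantity, "Difference in mean change from baseline in PhGA at Week 24 between treatments", and the rule probably reaches the MCTD model, since step 2 is singled out as being for SjS. But the visible SAP 2.5.2 and 2.6.2 specify SjS models only; the MCTD model stands in Protocol 12.4.2. MCTD also has no efficacy criteria.
- *There is no backup Week 24 analysis.* SAP 2.5.5 and 2.5.6 are redacted and may contain one. Of the raw data, SAP 2.5.1 says: "Descriptive statistics (raw and change from baseline) will be provided by treatment group and visit/time". Week 24 results would therefore remain visible, although the criteria apply to the model estimate.
- *SAP 5.4 contradicts 2.5.2 on covariance.* Compound symmetry is itself one of the other structures that 2.5.2 allows. Section 5.4 is narrower, not opposed.
- *The false-positive rate rises in general.* If the effect is zero at every visit, the reduced model is positive less often than planned (4–9% against 10%). The excess arises only when there is an effect earlier that has gone by Week 24.

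**Conclusion.** The point holds for the SjS primary analysis, as a minor one. If step 3 is reached, the rule as written yields a visit-averaged difference where the estimand and both criteria require Week 24. With complete data and assumed correlations of 0.4 to 0.8, the chance of meeting both criteria falls from about 81% to about 50% for a linear rise to 3.5. It goes from about 10% to about 53% for an early effect that is zero by Week 24. A constant effect loses nothing. These figures are conditional on a branch that is very unlikely to be used, and the stated sample size and power are unaffected.

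The same rule governs the SjS secondary models of SAP 2.6.2. Their fixed-effects list is partly redacted, so a stratification factor may be present there and would be removed first. Reach to MCTD is probable but cannot be confirmed from the visible SAP.

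**What to change.** In SAP 5.4 step 3, delete the five words naming the interaction, so that every fallback keeps it and only a stratification factor, where there is one, may be dropped. In line with SAP 2.5.2, list other covariance structures to try as well as compound symmetry before any fixed effect is removed.

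Add that if no model with the interaction converges, this will be reported, and a pooled-visit effect will not be labelled as Week 24. For SjS, a Week 24 ANCOVA adjusted for baseline ESSDAI may then be given as a last resort, with its limits stated. It is less efficient than the repeated-measures model. Because data after intercurrent events are set to missing (SAP 2.5.3), it also needs missingness to be explained by treatment and baseline alone, a stronger assumption than the one the repeated-measures model makes.

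The cost is five words deleted and a few sentences added. Nothing changes if the primary model converges.
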